## 8.2 EXAMINATION OF SUBGROUPS

For the primary efficacy endpoint (time to adjudicated clinical worsening event), subgroup analyses will be performed. These subgroups will include:

- Background PAH therapy (PDE5-I or sGC stimulator only versus ERA only)
- Etiology of PAH (idiopathic/heritable, associated with collagen vascular disease, and other etiologies)

- Baseline walk categories ( $\leq 350$  m versus  $> 350$  m)
- Baseline WHO FC (class 1-2 versus class 3-4)
- Age group ( $< 65$  years versus  $\geq 65$  years)
- Sex (male versus female)
- Maximum dose achieved ( $< 9$  mg versus  $\geq 9$  mg total daily dose)
- Geographic region, categorized as North America (United States and Canada), Asia-Pacific (China, Taiwan, India, Australia, Singapore, South Korea), Europe (Germany, United Kingdom, Israel, Italy, Netherlands, Poland, France, Denmark, Greece, Austria, and Sweden), and South and Latin America (Mexico, Brazil, Chile, and Argentina)

Similarly, the subgroup analyses for subgroups listed above will also be performed for the key secondary endpoint of change from Baseline in 6MWD at Week 24.

No adjustment for multiplicity will be performed for these subgroup analyses.

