Drug Dosage and Formulation	
Background Regimen: Every subject must have been receiving background monotherapy with one PAH-approved oral therapy for at least 30 days at randomization, and must have been receiving a stable dose for a minimum of 10 days at randomization. Once randomized, subjects must remain on the same dose of background oral PAH monotherapy for the duration of the study. In the event a subject must discontinue their background PAH oral therapy for any reason (e.g. AE), they must be switched to another agent within the same class of medication, if available and clinically appropriate per the Investigator's discretion. If no alternative therapy in the same class of medication is available and appropriate, the subject should be switched to a different class of approved oral PAH therapy.
 
The minimum dose of oral PAH therapy used during the study must comply with the approved prescribing information for the product.
 
Experimental Regimen: All subjects will receive oral treprostinil (UT-15C) sustained release tablets or matching placebo. Study drug may be provided in 0.125, 0.25, 0.5, 1, and 2.5 mg sustained-release tablets to be administered three times (TID) daily. The first dose of study drug (0.125 mg) should be taken by the subject at the study site within 10 minutes of consuming food. Oral dosing of study drug will then continue at 0.125 mg TID (every 6 to 8 hours) with food. Dose escalations can occur no more than every 24 hours (three consecutive doses) in 0.125 mg increments TID during the first four weeks of the study. Following 4 weeks of treatment, dose escalation may occur no more than every 24 hours in either 0.125 mg or 0.25 mg increments TID. The maximum dose allowed will be 12 mg TID. Note that sudden dose escalations or reductions may lead to intolerable adverse effects or worsening of PAH, respectively, and gradual dose titrations are recommended to reduce the risk to subjects. Placebo will be identical in size, shape, and color to the respective active tablets.

Control Group	Placebo with PAH-approved oral monotherapy
Route of Administration	Oral

Procedures

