6 DRUGS AND DOSING

6.1 DRUG DOSAGE, ADMINISTRATION AND SCHEDULE

The UT-15C tablets are sustained release osmotic tablets. Active treatment is UT-15C tablets provided as 0.125, 0.25, 0.5, 1, and 2.5 mg strengths. The 0.125, 0.25, 0.5, 1, and 2.5 mg tablets are colored blue, green, white, yellow, and pink, respectively. The formulation contains

pharmaceutically acceptable excipients used in other approved drug products. Placebo tablets are identical in size, shape, and color to the respective UT-15C tablets.

Once all entry criteria have been met and random treatment assignment confirmed, the first dose of study drug (0.125 mg) should be taken at the site by the subject immediately after (~10 minutes) consuming food. Oral dosing of study drug will be continued at 0.125 mg TID (every 6 to 8 hours) immediately after (~10 minutes) consuming food. Subjects must be instructed to take the appropriate amount of UT-15C tablets based upon their prescribed dose. Prior to the Week 4 visit, each dose of study drug should be adjusted in 0.125 mg increments every 24 hours as clinically indicated. Following the Week 4 visit throughout the remainder of the study, each dose of study drug may be adjusted in 0.125 or 0.25 mg increments every 24 hours as clinically indicated. The maximum allowable dose of study drug will be 12 mg TID.

Doses of study drug should continue to be increased in the absence of dose-limiting drug-related adverse effects, to ensure that each subject receives the optimal clinical dose throughout the study. [Table 6-1](#) provides a range of doses that may be reasonable targets for a subject to achieve by visit notwithstanding any AEs that limit dose escalation.

Table 6-1 Study Drug Goal Dose Titration Ranges

Study Week	Dose (mg) Three Times Daily
4	0.5 – 1.5
8	1.5 – 2.5
12	2.5 – 3.5
24	5.5 – 6.5

Dose changes should be conducted under appropriate medical supervision in consultation with the study site. Each dose of study drug is not required to be the same during titration. For example, doses of 1.125 mg morning, 1.125 mg afternoon, and 1.25 mg evening, are acceptable during titration. It is recommended that the difference between any of the three doses not exceed 0.125 mg prior to Week 4 or 0.25 mg after Week 4.

At least weekly telephone calls between site personnel and the subject should be made during the first 24 weeks of the study to monitor AEs and make decisions about dose titration. More

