Throughout the course of the study, the dose of study drug should continue to be increased at the discretion of the Investigator up to a maximum allowable dose of 12 mg TID. Dose escalation may be made less frequently or temporarily suspended if a subject experiences an intolerable AE that may worsen as a result of an increase in study drug dose. If an AE remains intolerable, the Investigator may decrease the dose of study drug. In the event of continued intolerable AEs, dose reductions may occur. The exact dose reduction and frequency of dose reduction should be based on the clinical condition of the subject and the severity/seriousness of the event. In general, dose reductions may occur in 0.125 mg or 0.25 mg increments every 12 to 24 hours.

Larger dose reductions may be necessary in the event of an emergency situation. If the subject is still experiencing an intolerable AE then the Investigator may temporarily or permanently withdraw the subject from study drug. Following temporary discontinuation of study drug, all attempts should be made to re-initiate study drug in affected subjects. Subjects should be re-started on study drug at a reduced dose or at 0.125 mg TID depending on the clinical condition of the subject, the subject's previous response to study drug, the dose at the time of discontinuation, and the duration of temporary discontinuation from study drug. Following restart of study drug, all efforts should be made to increase the dose until the desired clinical improvement in the subject's symptoms of PAH occurs.

Notwithstanding these study drug dosing guidelines, the well-being of each subject is paramount and all Investigators must act in accordance with the best medical interests of the subjects at all times during their participation in the study.

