### ***10.1.1.3 Sensitivity and Subgroup Analyses***

The primary efficacy analysis of time to adjudicated clinical worsening events will also be provided for the Per-protocol Population.

The following sensitivity analyses will be performed:

- For all subjects who drop out from the study early, they are considered as having a clinical worsening event. Time to event will be calculated from randomization to subject's discontinuation date.
- For all subjects who drop out from the study early due to AEs, they are considered as having a clinical worsening event. Time to event is calculated from randomization to subject's study discontinuation date.

The time from randomization to clinical worsening will also be compared between treatment groups using a Cox proportional-hazards regression model, adjusting for Baseline 6MWD category ( $\leq 350$  meters versus  $> 350$  meters) and background PAH therapy (as a categorical variable: PDE5-I/sGC stimulator or ERA). Hazard ratio and its 95% confidence interval will be calculated. SAS Procedure PHREG will be used and the pseudo SAS statements are listed below:

```
proc phreg;
  Model TimeToWorsening*Censor_Status(1) = treatment;
  Strata BGTX B_6MWD / risklimits ties=efron;
run;
```

where BGTX variable denotes the background therapy and B\_6MWD denotes the Baseline 6MWD category  $\leq 350$  meters versus  $> 350$ .

Subgroup analyses will be performed on the following factors: background PAH therapy, PAH etiology, Baseline WHO FC, age group (<65 years versus  $\geq 65$  years), Baseline 6MWD category, sex (male versus female), maximum dose achieved (<9 mg versus  $\geq 9$ mg total daily dose), and geographic region as specified in Section 8.2. The estimated hazard ratio between the active and placebo groups from this model will be calculated and displayed along with its 95% confidence interval on the summary and analysis table and plot.

Since clinical worsening is a composite endpoint, the following components of this composite endpoint will also be summarized and analyzed with the same approach as the composite endpoint:

- Time to death (all causes) during the study
- Time to hospitalization due to worsening PAH

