#### ***10.2.1.1 Sensitivity and Sub-group Analyses***

This methodology for key secondary efficacy analysis of change in 6MWD at Week 24 using MMRM will also be carried out with data up to Week 48 included in the model. The treatment effects at weeks 36 and 48 will be estimated.

With non-parametric analysis of covariance method, in order to analyze walk distances at each scheduled assessment, values for missing or excluded assessments up to Week 48 will be imputed according to rules described under “Missing data handling for 6MWD” in Section 8.3. Missing values beyond Week 48 will not be imputed. The visits beyond Week 48 will only be summarized using the observed values.

To further support the robustness and assess the sensitivity of efficacy analysis of change in 6MWD at Week 24, the above MMRM method will be repeated using each of the following modifications:

- MMRM model with the Per-Protocol Population
- MMRM model with only subjects achieve total daily dose  $\geq 9$  mg.

Analyses using non-parametric analysis of covariance will be repeated using each of the following modifications (as data permit):

- With the Per-Protocol Population
- Using only the observed values without imputation
- Including data collected after termination of the study drug
- Analyses will be carried out within PAH etiology categories
- Analyses will be carried out within Baseline WHO FC categories
- Analyses will be carried out within PAH background therapy categories
- Analyses will be carried out within Baseline 6MWD categories ( $\leq 350$  meters versus  $> 350$  meters)

- Analyses will be carried out within geographic regions
- Analyses will be carried out within sex
- Analyses will be carried out within age group (<65 years versus ≥65 years)
- Analyses will be carried out by study drug dose at Week 24 (total daily dose <9 mg and ≥9 mg)
- Analyses will be carried out within UT-15C dose quartile at Week 24
- Plot of 6MWD at Week 24 by UT-15C dose

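### Maximum dose achieved (<9 vs ≥9 mg/day) is a post-randomisation variable; its subgroup hazard ratios are not randomised comparisons and it should leave the subgroup lists and forest plots

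*SAP*

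**What the plan says.** SAP 8.2 names eight subgroup factors for time to adjudicated clinical worsening. Seven are baseline characteristics or geographic region. The other is "Maximum dose achieved", split at 9 mg total daily dose. SAP 10.1.1.3 repeats it within the same list ("sex (male versus female), maximum dose achieved") and says: "The estimated hazard ratio between the active and placebo groups from this model will be calculated and displayed", with a 95% confidence interval, in a table and a plot (Table 14.2.1.5, Figure 14.2.1.6). SAP 8.5 measures time from randomisation.

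SAP 8.2 extends the list to walk distance: "the subgroup analyses for subgroups listed above will also be performed for the key secondary endpoint", namely change in 6MWD at Week 24. SAP 10.2.1.1 uses a different variable for that endpoint: "Analyses will be carried out by study drug dose at Week 24". It also offers an MMRM restricted to subjects who reach at least 9 mg/day as one of the analyses meant to support robustness.

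The Protocol determines when the class can be known. The Synopsis says "Dose escalations can occur no more than every 24 hours (three consecutive doses) in 0.125 mg increments TID" during the first four weeks. Section 6.1 has the same step size ("each dose of study drug should be adjusted in 0.125 mg increments every 24 hours"). It also says: "Dose escalation may be made less frequently or temporarily suspended if a subject experiences an intolerable AE".

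The only caveat in SAP 8.2 is that subgroups are not adjusted for multiplicity. Neither document gives a landmark, a time-dependent dose term or a non-randomised label for this factor, or says how placebo subjects are classed.

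**The concern.** A subgroup hazard ratio is a randomised comparison only if the subgroup is fixed at, or unaffected by, randomisation. This one fails in three ways.

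- **Time at risk.** A subject must remain event-free and on drug long enough to reach 9 mg/day, so early events always fall in the <9 mg class (immortal time).
- **Tolerability.** Escalation is slowed or stopped for adverse events, which treatment itself affects. The two arms therefore select different kinds of subject into the same class.
- **Placebo rule.** The likeliest reading is that placebo subjects are classed by their own titrated dose: SAP 12.1 summarises maximum study drug dose by treatment group, and Protocol 1.2.4 reports a placebo maximum for TDE-PH-308. Under that reading, balance is assured only if both arms titrate alike and dose relates to prognosis alike. If all placebo subjects were the comparator, bias would arise even with identical titration.

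For Week 24 6MWD the problem is selection rather than immortal time.

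At stake is a forest plot row that can show a false benefit, a false harm or a false dose pattern beside valid baseline rows. Misreading is a real risk: Protocol 1.2.4 already reads a post-hoc dose split in TDE-PH-301 as a stronger treatment effect at higher doses.

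**Working it through.** **1. The plan's event rate.** A placebo median of 32 months (SAP 5) gives a hazard of ln 2/32 = 0.02166 per month. The 12-month event rate is 1 − exp(−0.02166 × 12) = 22.9%, matching the plan's 23%.

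**2. Earliest possible entry to the ≥9 mg class.** 9 mg/day is 3 mg TID. Starting at 0.125 mg TID on Day 1, the number of steps is (3 − 0.125)/0.125 = 23. At one step per 24 hours this is Day 24. The Week 12 goal range (Protocol Table 6-1) is 2.5–3.5 mg TID, or 7.5–10.5 mg/day, which straddles the cut.

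**3. Placebo events by then,** 1 − exp(−0.02166 t), with 305 per arm (610/2):
- 23 days: 1.6% (5 subjects)
- Week 12: 5.8% (18)
- Week 24: 11.3% (34)

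**4. How far the arms may differ.** In TDE-PH-308 the maximum dose was 3.1 (SD 1.9) mg BID on UT-15C and 6.1 (SD 3.6) mg BID on placebo. 9 mg/day is 4.5 mg BID. With a normal shape, P(≥4.5) is 1 − Φ(1.4/1.9) = 0.23 and 1 − Φ(−1.6/3.6) = 0.67. With a lognormal shape it is 0.17 and 0.61. So about 17–23% of UT-15C and 61–67% of placebo subjects would have reached the cut in 16 weeks.

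**5. Simulation with a true hazard ratio of 1.00.** From the plan: marginal median 32 months, 36-month accrual, 48-month study, 10% dropout (placed at 30 months, the mean potential follow-up, 48 − 36/2). Assumed: time to 9 mg/day is 23 days plus a lognormal delay (log SD 0.5). Where dose is linked to prognosis, log-hazard SD is 0.7 and the correlation of ability to reach the dose with low hazard is +0.4 (healthier subjects reach it more often) or −0.4. The first four rows split the 23%/67% gap in different ways between ability to reach the dose and speed. Entries are hazard ratios, ≥9 mg / <9 mg, with placebo classed by its own dose.

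| Scenario (% able UT-15C/placebo; median months) | No link | +0.4 | −0.4 |
|---|---|---|---|
| Ability only (23/68; 2.0/2.0) | 1.00 / 0.86 | 0.81 / 0.74 | 1.21 / 0.94 |
| Speed only (90/90; 4.8/2.9) | 0.89 / 1.13 | 0.88 / 1.07 | 0.88 / 1.14 |
| Mixed (60/90; 4.1/2.9) | 0.93 / 0.61 | 0.82 / 0.55 | 1.02 / 0.62 |
| Mixed (45/80; 3.6/2.5) | 0.93 / 0.78 | 0.82 / 0.69 | 1.05 / 0.81 |
| Equal titration (90/90; 3/3) | 1.00 / 1.01 | 1.00 / 1.00 | 1.00 / 1.01 |

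The overall hazard ratio was 1.00 throughout.

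Two further cases, with equal titration in both arms:
- Link to prognosis in one arm only: 0.85–1.18 in either class.
- All placebo subjects as comparator: 0.79–0.86 (≥9 mg) and 1.94–2.90 (<9 mg).

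A second simulation with different assumptions (follow-up 12–48 months; 50% of UT-15C able at about Week 16 and 85% of placebo at about Week 8, plus one equal-titration case; log-hazard SD 0.8 and correlation ±0.5 where linked) gave 0.68–1.15 and 0.63–1.01, again with a true hazard ratio of 1.00.

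**6. Would a Week 24 landmark repair it?** In the first four scenarios it gives about 1.00 when dose is unrelated to prognosis. With correlation ±0.4 it gives 0.81–1.23 (own dose) or 0.71–1.35 (all placebo). It removes immortal time but not selection.

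**The case against.** This is one of eight unadjusted subgroup factors, and its name shows that it is an on-treatment variable. Strictly unavoidable immortal time is small: 1.6% of placebo subjects have an event before Day 24, and the Week 12 figure is not structural because faster titration is allowed. With no prognosis link, the calibrated ≥9 mg hazard ratios are only 0.89–1.00. With, say, 100 events in that row, the 95% interval spans a factor of exp(1.96 × 2/√100) ≈ 1.5 either way, so noise would exceed the bias.

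The calibration comes from a 16-week BID trial. This trial is TID, lasts years, starts at 0.125 mg and is intended to improve titration (Protocol 1.4). The open-label study TDE-PH-304 reports mean doses of 3.9 mg BID at 1 year and 4.5 mg BID at 2 years, which fits poorly with only 23% ever reaching 9 mg/day. The simulation also does not model unequal stopping of study drug by arm. Finally, the sponsor has a legitimate interest in dose.

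Much of this stands as a limit on the size. It does not restore the comparison. The <9 mg row is distorted even without a prognosis link (0.61–1.13). Equal titration is not assured, and the one within-program trial that reports maximum dose by arm shows a twofold difference in means. Interest in dose is better served by an analysis labelled for what it is.

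**Conclusion.** The concern holds. Maximum dose achieved depends on time at risk and tolerability, and its distribution probably differs by arm, so its subgroup hazard ratios are not randomised comparisons and can err in either direction.

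How large the error would be is uncertain. Over the calibrated scenarios the hazard ratios run from 0.81 to 1.21 (≥9 mg) and from 0.55 to 1.14 (<9 mg) when the truth is 1.00. These depend on assumed titration speeds, shares able to reach the dose, frailty and correlation, none of which is in the documents. There is no bias if titration and its link to prognosis are the same in both arms.

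The 205-event design, the primary log-rank test, the interim and final alpha and the key secondary hierarchy are untouched. The change should be made before unblinding, but the trial's main conclusion does not depend on it.

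**What to change.** - Remove maximum dose achieved from the lists in SAP 8.2 (primary endpoint and Week 24 6MWD) and 10.1.1.3, from Table 14.2.1.5, and from forest plots 14.2.1.6 and 14.2.2.2. This also settles the mismatch with 10.2.1.1 over which dose variable applies to 6MWD.
- In 10.2.1.1, do not present the ≥9 mg MMRM (Table 14.2.2.3) as robustness evidence. Label it, the Week 24 dose split, the dose quartiles and the dose plot (Tables 14.2.2.14 and 14.2.2.15, Figure 14.2.2.1) as non-randomised and exploratory.
- An exposure-response analysis is optional and belongs outside the forest plot. If a Week 24 landmark is used, state the placebo rule and say that it removes immortal time only.

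The required changes are wording, with no new data or programming and no loss of power. The sponsor gives up an easily quoted subgroup result.

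The optional landmark costs more. It drops about 11% with an event by Week 24 at the placebo rate, or 1 − 0.887 × 0.981 = 13% once the plan's dropout is added. Subjects who stop drug are also censored (SAP 10.1.1.2). If stopping as in TDE-PH-301 recurred (22% vs 14% over 16 weeks), a constant rate would give 1 − 0.78^1.5 = 31% vs 1 − 0.86^1.5 = 20% by Week 24. The loss may be smaller, since that trial had no adverse-event discontinuations among the 23 subjects who had the 0.25 mg tablet from randomisation.

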### 8.3 PREMATURE DISCONTINUATION AND MISSING DATA

Clinical worsening events are evaluated up to the end of the study. In this event-driven study, at the end of the study, some subjects will not have clinical worsening events; some will discontinue the study early or be lost-to-follow-up before experiencing a clinical worsening event. For the time to clinical worsening event data, a censoring algorithm will be employed.

The 6MWD and other secondary efficacy endpoints are evaluated up to the end of the study; however, the analyses are mainly focused on the data up to Week 48. For 6MWD and other key secondary efficacy endpoints, missing data will be imputed as described in the sections below.

#### 8.3.1 *Missing Data Handling for Time to Clinical Worsening*

For the analysis of time to clinical worsening, subjects who do not have an adjudicated clinical worsening event will be censored at the time of their last known study drug dose. For subjects who are reported as having a clinical worsening event by the Investigator and subsequently are classified as not having a clinical worsening event by the adjudication committee, the time to clinical worsening is also censored at the time of their last assessment date. For subjects who dropped out of the study early without experiencing a clinical

worsening event, the subjects will be censored at the time of their last assessment prior to down-titration or discontinuation of study drug.

In addition, the following 2 additional analyses will be performed on the primary efficacy endpoint (adjudicated time to clinical worsening) to assess the impact of missing data:

1. Early termination treated as clinical worsening event
2. Early termination due to AEs treated as clinical worsening events

For the mortality analysis, the vital status (live/dead status) for all subjects will be collected throughout the study to the study closure (the last patient last visit). Vital status for subjects who discontinued the study early is included in this mortality analysis. If the vital status is unknown at study closure, the time to death will be censored at the last known date the subject is alive.

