## 8.5 DERIVED AND TRANSFORMED DATA

Time to Clinical Worsening will be derived as follows:

Parameter	Scenario	Formula	Status
Time to Clinical Worsening (weeks)	Subjects with clinical worsening event reported during the study that is adjudicated/confirmed	= (Worsening date – Randomization date)/7 Note: for subjects with clinical worsening due to worsening 6MWD, the clinical worsening date is date of the second/confirmatory 6MWT	0 (event)
	Subjects who died during the study	= (Death date – Randomization date)/7	0 (event)
	Subjects with clinical worsening event reported during the study that is adjudicated as not meeting the clinical worsening event criteria by the adjudication committee	For analysis of investigator reported clinical worsening event: = (Worsening date – Randomization date)/7	0 (event)
		For analysis of adjudicated clinical worsening event: = (Last assessment date – Randomization date)/7	1 (censored)
	Subjects without clinical worsening event during the study	= (Last assessment date – Randomization date)/7	1 (censored)
Subjects discontinued from the study prematurely that did not have a clinical worsening event	= (Last assessment date – Randomization date)/7	1 (censored)	

For subjects with clinical worsening due to the decrease from Baseline in 6MWD, confirmatory 6MWT should be conducted. The event time is based on the date of the

confirmatory 6MWT. As a sensitivity analysis, the event time based on the date of the first reported 6MWT will also be performed.

Hemodynamic parameters will be derived as follows:

Parameter	Formula
Cardiac index in L/min/m 	= cardiac output (CO) Fick / body surface area (BSA)
Systemic vascular resistance (SVR) in dynes*sec/cm 	=80 * (systemic arterial pressure mean [SAPm] – right atrial pressure mean [RAPm]) / CO Fick
SVR index (SVRI) in dynes*sec/cm  /m 	=80 * (SAPm – RAPm) / cardiac index
Pulmonary vascular resistance (PVR) in dynes*sec/cm 	=80 * (Pulmonary artery pressure mean [PAPm] – Pulmonary capillary wedge pressure mean [PCWPm]) / CO Fick
PVR Index (PVRI) in dynes*sec/cm  /m 	=80 * (PAPm – PCWPm) / cardiac index

Electrocardiogram parameters will be derived as follows:

Parameter	Formula
QTc (Bazett)	$= QT / \sqrt{\frac{60}{HR}}$
QTc (Fridericia)	$= QT / \sqrt[3]{\frac{60}{HR}}$

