#### ***10.1.1.2 Primary Efficacy Analyses***

Data on the Clinical Worsening Assessment page of the eCRF will be used in determining clinical worsening status. Investigator-reported clinical worsening events will be reported directly from the eCRF data, regardless of the outcome of the adjudication committee review. An independent adjudication committee will be utilized to adjudicate all investigator-reported clinical worsening events. Adjudicated clinical worsening events will be reported using data received from the adjudication committee.

Subjects who discontinue study drug for reasons other than clinical worsening will be censored at the time of discontinuation of the study drug. Non-fatal clinical worsening events that occur more than 7 days after permanent study drug discontinuation will not be included in the summary and analysis of clinical worsening events. However, all deaths within the study follow-up period (30 days after the last study drug dose) will be included as clinical worsening events. Time to clinical worsening will be summarized by treatment group using product-limit estimates calculated by the Kaplan-Meier method, and displayed graphically as Kaplan-Meier curves. A tabular summary of this analysis will include the number of subjects at risk (sample size), estimated median duration, and a 95% confidence interval for the median duration for each treatment group.

For the primary efficacy analysis of time to adjudicated clinical worsening, the log-rank test adjusted for the type of background therapy (PDE5-I or sGC stimulator versus ERA) and the Baseline 6MWD ( $\leq 350$  meters versus  $> 350$  meters) will be used to calculate the p-value for treatment differences in the ITT Population.

The SAS Procedure LIFETEST will be used. The pseudo SAS statements are listed below:

```
proc lifetest;
  time TimeToWorsening*Censor_Status(1);
  strata BGTX B_6MWD / group=Treatment test=all;
run;
```

where BGTX variable denotes the background therapy and B\_6MWD denotes the Baseline 6MWD category ( $\leq 350$  meters versus  $> 350$  meters).

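### Primary-endpoint censoring rules in SAP 8.3.1, 8.5 and 10.1.1.2 contradict each other, and protocol 10.8 drops rejected-event subjects whom the SAP keeps

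*SAP*

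**What the plan says.** **Censoring.** SAP 8.3.1 opens with a general rule: "subjects who do not have an adjudicated clinical worsening event will be censored at the time of their last known study drug dose". For events that the adjudication committee rejects, it adds that "the time to clinical worsening is also censored at the time of their last assessment date". For early drop-outs without an event, it uses "their last assessment prior to down-titration or discontinuation of study drug". In the SAP 8.5 table every censored row runs to the last assessment date, including the row for "Subjects discontinued from the study prematurely that did not have a clinical worsening event". SAP 10.1.1.2 has a further rule: "Subjects who discontinue study drug for reasons other than clinical worsening will be censored at the time of discontinuation of the study drug".

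**Events.** SAP 8.5 gives event status to "Subjects with clinical worsening event reported during the study that is adjudicated/confirmed" and to "Subjects who died during the study", with no limit after drug stop. SAP 10.1.1.2 says "Non-fatal clinical worsening events that occur more than 7 days after permanent study drug discontinuation will not be included", but counts deaths up to 30 days after the last dose.

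**Rejected events.** Protocol 10.8 says that a subject whose event the committee does not accept is left out of the analysis. Protocol 10.3 runs all efficacy analyses on the ITT population, and SAP 8.3.1 and 8.5 keep the subject as censored.

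**Off-drug follow-up.** Protocol 3.2.1.1 assesses worsening until the last study visit. Protocol 7.4 and Table 3-1 (footnote m) encourage subjects who stop drug before Week 24 to attend visits up to Week 24.

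**The concern.** The SAP should fix each subject's event status and time before anyone sees treatment codes. Here a programmer cannot build one primary dataset that obeys every stated rule, and no section is said to prevail.

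Three things are at stake. First, the date: last dose, drug stop and last assessment can lie months apart for a subject who stops early and keeps attending. Second, SAP 10.1.1.2 does not match events to time at risk. After drug stop, a subject who dies within 30 days stays in the risk set until death, while an event-free subject left it at drug stop. Third, protocol 10.8 taken literally is an exclusion after randomization that depends on outcome.

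A secondary point is that SAP 8.5 has no post-drug cut-off and SAP 10.1.1.2 has one. The latter is probably meant to qualify the former, but neither section says so.

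**Working it through.** **Step 1. The plan's own figure.** Inputs from protocol 10.2: 205 events, hazard ratio 0.62, 1:1 allocation, final two-sided alpha 0.044. Schoenfeld power is Φ(|ln 0.62| × √205 / 2 − z) = Φ(0.478 × 7.159 − 2.014) = Φ(1.408) = 92.0%; at alpha 0.05 it is 92.8%. Both agree with the stated minimum of 90%, so the sample size is not in question.

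**Step 2. The rules applied to invented subjects.** In every case the termination visit is on day 60, the last dose on day 67 after down-titration, and the Week 24 visit (if reached) on day 168. Time is days from randomization divided by 7, as in SAP 8.5.

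| Subject | SAP 8.3.1 | SAP 8.5 | SAP 10.1.1.2 |
|---|---|---|---|
| A: event-free, attends Week 24, then leaves | censored at 67/7 = 9.6 (first rule) or 60/7 = 8.6 (drop-out rule) | censored at 168/7 = 24.0 | censored at 9.6 |
| B: as A, with adjudicated PAH hospitalization on day 90 | not addressed | event at 90/7 = 12.9 | not counted (90 − 67 = 23 days, over 7) |
| C: dies on day 80 | not addressed | event at 80/7 = 11.4 | event at 11.4 (13 days after last dose) |
| D: event rejected, last assessment day 60 | 9.6 (first rule) or 8.6 (rejected-event rule) | 8.6 | no separate rule |

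Subject A has three different times. Subject C is counted beyond the date at which A is censored under the same section. Subject D is absent altogether under protocol 10.8. For deaths, a conflict between 8.5 and 10.1.1.2 is only arguable, because SAP 12.3 describes the study period as including 30 days after the last dose.

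**Step 3. How many subjects change event status at the plan's drop-out.** Protocol 10.2 assumes 10% drop-out by the end of the study, which gives 30.5 per arm at N = 610 and 42.5 at N = 850. Assumptions: these are drug stops, they are spread evenly over 48 months (protocol 3.5 estimates 4 years), visits to Week 24 are complete, and 20% of events are fatal. The placebo hazard is ln 2 / 32 = 0.02166 per month. Week 24 is 5.52 months and 7 days is 0.23 months, so off-drug time beyond day 7, summed over stopping times, is (5.52 − 0.23)² / 2 = 13.99.

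- N = 610: 30.5/48 × 13.99 × 0.02166 × 0.80 = 0.15 per arm.
- N = 850: 42.5/48 × 13.99 × 0.02166 × 0.80 = 0.21 per arm.
- At three times the placebo hazard: 0.46 and 0.64.

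This slightly overstates the count, because it ignores subjects who have an event before stopping. Allowing for that gives 0.14 and 0.20, or 0.40 and 0.55 at three times the hazard.

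**Step 4. Effect on the hazard ratio.** This was simulated with 1,200 runs per cell, exponential times, 36-month uniform accrual and a cut at the 205th event counted under SAP 10.1.1.2. At the plan's drop-out, counting events to Week 24 moves the mean hazard ratio by at most 0.0015 (for example 0.623 to 0.624). The censoring date alone moves it by 0.0001 or less.

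**Step 5. Stress case, not the plan's figures.** Suppose 22% (UT-15C) and 14% (placebo) stop within 6 months, N = 850. Those rates come from the 16-week twice-daily study TDE-PH-301 in protocol 1.2.4, which began with a 1 mg starting dose, so they are probably high. Counting events to Week 24 then moves the hazard ratio from 0.619 to 0.630 at the placebo hazard, and from 0.630 to 0.670 at three times it. Across the early-stopping cells run, the censoring date alone moves it by at most 0.009.

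**The case against.** The best defence is that the specific qualifies the general. SAP 8.5 is a table of formulas, and SAP 10.1.1.2 is the primary-analysis section with an express limit. Likewise, the first sentence of 8.3.1 can be a general rule and the next two its exceptions. For event status this is probably right, which is why that point is secondary. It does not settle the censoring date: the 8.3.1 exceptions, 8.5 and 10.1.1.2 still name different dates for one early stopper.

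The dates will also often be close, because the termination visit precedes down-titration (protocol 7.4). That holds for most subjects, but not for those who stop before Week 24 and keep attending.

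The SAP also plans two analyses that recode early terminations as events, and an analysis of death at study closure. Those stand and should stay. They impute events or cover deaths only; none counts actual non-fatal events after the 7-day cut-off.

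Three stronger readings are tempting, and the documents do not support them.

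- A reader might infer that rejected-event subjects will be deleted. If 10% to 20% of reported events were rejected (an assumption), that would be 205 × 0.10/0.90 ≈ 23 to 205 × 0.20/0.80 ≈ 51 subjects, with a hazard ratio near 0.61. The SAP keeps them, so no such analysis is planned.
- A reader might infer biased results or lost power. The Step 5 shifts need heavy early stopping and a raised off-drug hazard, neither of which the plan states. At the plan's drop-out about one event in 205 is affected.
- A reader might infer that the 154- and 205-event triggers are undefined, or that the choice will be made after unblinding. SAP 4.2 places the interim details in a separate SAP, which may settle the triggers, and nothing shows that the choice stays open.

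**Conclusion.** The point holds as a contradiction in the text. The censoring dates in SAP 8.3.1, 8.5 and 10.1.1.2 cannot all be applied to the same subject. SAP 10.1.1.2 counts events past its own censoring date, and protocol 10.8 conflicts with protocol 10.3 and the SAP. The missing cut-off in SAP 8.5 is an unstated qualification rather than a firm conflict.

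The likely numerical effect is negligible. That rests on the Step 3 assumptions, chiefly that the plan's study drop-out figure stands in for drug discontinuation, for which this trial's documents give no rate. The reason to act is that the correction is cheap and removes a choice from the confirmatory endpoint, not that the result is likely to change. Severity: minor to should-fix.

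**What to change.** Before unblinding:

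1. State one event-counting rule and one censoring date per scenario, identical in SAP 8.3.1, 8.5 and 10.1.1.2, with every ITT subject kept. Censor event-free and rejected-event subjects at the earlier of the last ascertainment of worsening status and the end of the counting window. Use a common window for fatal and non-fatal events, because one censoring date cannot fit both 7 and 30 days. If the two windows are kept, say how days 8 to 30 are handled and add a common-window check. The 30-day contact in protocol 3.5 confirms survival only, so a common 30-day window would have incomplete non-fatal data. Add the window to the SAP 8.5 table, including the death row.
2. In protocol 10.8, replace the exclusion with: *the event is not counted; the subject remains in the ITT analysis*.
3. If a post-drug cut-off stays primary, add one pre-specified supportive analysis that counts every adjudicated event found while the subject is still assessed, including up to Week 24 after drug stop. Keep the two early-termination analyses and the death-at-closure analysis beside it.

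The cost is aligned SAP wording, one protocol sentence and one extra table (a second if the common-window check is needed), with no new data collection. The downsides are that off-drug visits are only encouraged, so follow-up will be incomplete, and that the supportive hazard ratio may be slightly less favourable.
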